11.4 Follow Up of Adverse Events/Serious Adverse Events

All AEs/SAEs documented at a previous visit/contact that are designated as not recovered will be reviewed by the Investigator at subsequent visits/contacts.

All AEs will be followed until the resolution of AE, completion of the patient's participation, or study termination, whichever occurs first.

Serious AEs will be followed until resolution, the condition stabilizes, or the Investigator and Sponsor agree that follow up is no longer necessary. Rules for AE/SAE follow up apply to all patients, including those withdrawn from the study prematurely to the extent allowed by the patient's consent. The Investigator will ensure that follow up includes further investigations consistent with appropriate medical management and patient consent to determine the nature and/or causality of the AE/SAE.

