11.1 Definition of Adverse Events

11.1.1 Adverse Event (AE)

An AE is any untoward medical occurrence in a clinical study patient, whether or not the event is considered causally related to the investigational product. An AE can be a new occurrence or an existing process that increases significantly in severity or frequency.

Adverse events include:

- Symptoms described by the patient or signs observed by the Investigator or medical staff
- Test abnormalities (laboratory tests, ECG, x-rays, etc.) that result in an alteration in medical care (diagnostic or therapeutic)
 - Abnormally low values for C3, C4 or A:G ratio may result in discontinuation of study treatment. Patients who discontinue due to these laboratory test abnormalities will be classified as “withdrawals due to adverse events” and a narrative describing their history and reason for withdrawal will be prepared by the Investigator.
 - Abnormally low eGFR or platelet count or abnormally high urine protein as described in Table 3 may result in discontinuation of study treatment. Patients who discontinue due to these laboratory test abnormalities will be classified as “withdrawals due to adverse events”.
- Injury or accidents. Note that if a medical condition is known to have caused the injury or accident (a fall secondary to dizziness), the medical condition (dizziness) and the accident (fall) should be reported as 2 separate AEs. The outcome of the accident (hip fracture secondary to the fall) should be recorded in source documents.

Abnormalities present at Baseline are considered AEs only if they reoccur after resolution or worsen in severity or frequency during the study.

Each AE is to be classified as serious or nonserious.

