11.2.7 Outcome of AEs

If possible, AEs will be followed until resolved (synonyms: recovered, recuperated, ended) either with or without sequelae, or the Investigator assesses them as chronic or stable.

The outcome of each event (including date and time) will be described using the following categories:

- **Recovered:** The event resolved and patient returned to baseline
- **Recovered With Sequelae:** The event resolved but the patient is left with residual problems (e.g., functional deficits, pain)

- **Not Recovered:** At the last observation, the event was unchanged
- **Death (Fatal):** To be used for the one AE which, in the judgment of the Investigator, was the primary cause of death
- **Unknown:** There were no observations after the onset (initial observation or report) of the event

A patient withdrawn from the study because of an AE must be followed by the Investigator until clinical recovery is complete and laboratory results have returned to normal, or until progression has been stabilized. Follow-up may need to continue after the patient has discontinued from the study, and additional investigations may be requested by the Investigator. (see Section 11.4 for additional details on AE/SAE follow-up requirements).

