12 WITHDRAWAL OF PATIENTS

All patients who receive study drug should remain in the study whenever possible. However, patients are free to withdraw consent and/or discontinue participation in the study at any time, without prejudice to further medical care.

A patient's treatment and participation in the study may also be discontinued at any time at the discretion of the Investigator, CRO Medical Monitor, or Idera. Justifiable reasons to discontinue a patient from treatment and the study may include, but are not limited to the following:

- The patient was erroneously included in the study (i.e., did not meet eligibility criteria)
- The patient experiences an SAE assessed as possibly or probably related to study drug
- The patient is unable to comply with the requirements of the protocol
- The patient participates in another investigational study
- The patient withdraws consent
- The patient becomes pregnant
- A patient for whom the blind is intentionally broken

Patients who are withdrawn from treatment should complete the EOT/ET Visit 26/Week 25 assessments within 5 days of notification of withdrawal and the EOS Visit 27/Week 29 at 4 weeks (\pm 4 days) after the ET Visit (see Sections 10.1.4 and 10.1.5 for information regarding the EOT/ET and EOS Visits, respectively). A patient who completes the initial portion of the study (through the EOT Visit 26/Week 25) and is then lost to follow-up will not be considered to have prematurely withdrawn.

A patient will be considered "discontinued due to an AE" if they withdraw from the study due to any AE, regardless of whether or not the AE is considered related to investigational product. If the patient withdraws from the study due to an AE, the Investigator should arrange for the patient to be followed appropriately until the AE has resolved or stabilized (in the opinion of the Investigator).

The Investigator will document the reason(s) for treatment or study discontinuation on the eCRF. Idera and the CRO Medical Monitor should be informed when a patient is withdrawn from the study.

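### Section 11.4 has no exception for adverse events that led to withdrawal, which 11.2.7 and 12 require to be followed to recovery or stabilisation; separately, 10.1.5 counts the End-of-Study visit from the last dose instead of from EOT/ET

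*Protocol*

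**What the plan says.** **AE follow-up.** Protocol 11.4 opens with a rule for AEs in general: "All AEs will be followed until the resolution of AE", or until completion of the patient's "participation, or study termination, whichever occurs first". Serious AEs then get their own, longer rule, so the first rule in effect governs non-serious events. The section adds: "Rules for AE/SAE follow up apply to all patients, including those withdrawn from the study prematurely", as far as consent allows. Section 6.3.1 ends participation when the last visit is complete.

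Section 11.2.7 has a separate rule for AE withdrawals. Such a patient "must be followed by the Investigator until clinical recovery is complete and laboratory results have returned to normal"; stabilisation of the condition is the alternative end point. The section continues: "Follow-up may need to continue after the patient has discontinued from the study". It then sends the reader elsewhere: "see Section 11.4 for additional details on AE/SAE follow-up requirements". Section 12 says that the investigator should arrange for such a patient to be "followed appropriately until the AE has resolved or stabilized".

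Section 11.1.1 brings the Table 3 laboratory stops under this heading: "Patients who discontinue due to these laboratory test abnormalities will be classified as" withdrawals due to adverse events.

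**EOS visit.** Section 10.1.5, headed Visit 27/Week 29, places EOS 4 weeks (± 4 days) after the last dose. The synopsis, Schedule of Events footnote 3, and Sections 6.2, 6.3.1, 10.1.4 and 12 place it 4 weeks after the EOT or ET visit; footnote 3, 10.1.4 and Section 12 give a ± 4 day window.

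**Cross-references.** Sections 6.3.2, 8.3.5, 8.3.6 and 11.2.3 cite Section 11.5 for withdrawal or discontinuation. Section 11.5 covers pregnancy, overdose and similar reportable events. The withdrawal text is in Section 12.

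**The concern.** The two AE rules give different answers for one kind of patient: someone withdrawn because of a non-serious AE that is still open at the last visit. Under 11.4 follow-up may stop there; under 11.2.7 and 12 it must go on. A site that reads 11.2.7, follows its pointer to 11.4 and applies what it finds could stop too early.

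The Table 3 laboratory stops are the case that matters most. Low C3 or C4 together with a low A:G ratio stops study drug and starts early termination. An asymptomatic laboratory value need not meet any criterion in 11.1.2 for a serious event, so the longer rule for serious AEs would not necessarily catch it.

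The EOS anchor matters because Section 11 records AEs on the case report form through EOS. A site that works from 10.1.5 closes that window early, in a trial whose first primary objective is safety and tolerability.

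**Working it through.** **1. AE follow-up: the texts side by side**

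Take a non-serious AE that caused withdrawal and is unresolved at the last visit.

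| Section | Applies to | Follow-up ends |
|---|---|---|
| 11.4, general rule | All AEs; withdrawn patients included | Earliest of resolution, end of participation, study termination |
| 11.4, serious AEs | Serious AEs only | Resolution, stabilisation, or agreement of investigator and sponsor |
| 11.2.7 | Patients withdrawn because of an AE | Recovery with normal laboratory results, or stabilisation; may run past study exit |
| 12 | Patients withdrawn because of an AE | Resolution or stabilisation |

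For this patient 11.4 ends at the last visit at the latest, while 11.2.7 and 12 have no fixed end date. No figure can be computed for the difference. For serious AEs, and for AEs that resolve before the last visit, the rules do not conflict in this way.

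**2. EOS date: reproducing the protocol's own figures**

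Inputs: first dose on Day 1; 24 weekly doses; EOT 7 ± 2 days after the last dose (6.2, 6.3.1); EOS 28 ± 4 days after its anchor; 28 days of screening.

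- Last dose: 1 + 23 × 7 = Day 162 (Week 24).
- EOT: 162 + 7 = Day 169 (Week 25).
- EOS counted from EOT: 169 + 28 = Day 197 (Week 29). Participation: 4 + (197 − 1)/7 = 32 weeks.
- EOS counted from the last dose (10.1.5): 162 + 28 = Day 190 (Week 28). Participation: 4 + (190 − 1)/7 = 31 weeks.

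The stated Week 29 and approximately 32 weeks reproduce only with the EOT anchor. The nominal difference for completers is 197 − 190 = 7 days.

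**3. Windows, in days after the last dose (completers)**

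- 10.1.5: 28 ± 4, that is 24 to 32.
- Other sections: EOT on days 5 to 9, plus 24 to 32, that is 29 to 41.
- Days 24 to 28, which are 5 of the 9 days that 10.1.5 allows, fall before the earliest day the other sections allow.

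**4. Can one visit satisfy both rules?**

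Let e be the day of EOT/ET after the last dose. The other sections then allow e + 24 to e + 32. The days shared with 24 to 32 number max(0, 9 − e).

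| e | Other sections | Days meeting both |
|---|---|---|
| 5 | 29–37 | 4 (29–32) |
| 7 | 31–39 | 2 (31–32) |
| 8 | 32–40 | 1 (32) |
| 9 | 33–41 | 0 |

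Day 9 is within the allowed EOT window, so a site can be on schedule at EOT and still have no day that meets both rules.

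For patients who stop early the nominal difference is (e + 28) − 28 = e days, and again no day meets both rules once e is 9 or more. The protocol does not fix e for these patients: it limits the time from notification of withdrawal to ET (5 days), not the time from the last dose. No range is therefore given.

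**The case against.** **A specific rule governs a general one.** Section 11.2.7 is specific and mandatory, and Section 12 agrees with it. The sentence in 11.4 about withdrawn patients is not expressly confined to 11.4's own rules and could equally carry 11.2.7 to them. This largely stands: 11.2.7 was probably meant to govern. What remains is that 11.2.7 itself points to 11.4 for details, and 11.4 states a limit with no exception.

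**Other text reduces the risk.** Section 10.1.6 allows unscheduled visits to follow up AEs. Section 11.3 still requires reporting of serious AEs after EOS if the investigator sees a reasonable causal relationship. Table 3 and Section 8.3.4 bring the Patient Safety Committee, with both medical monitors, into abnormal-laboratory cases. These make an unnoticed early stop less likely, but none sets how long a non-serious AE is followed.

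**The EOS slip is isolated.** Section 10.1.5 stands alone against the Schedule of Events and several sections, and its own heading contradicts it. This stands: the intended timing is not in doubt. Section 12 nevertheless refers sites to 10.1.5 for EOS information, so the wrong anchor should not stay there.

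**Stronger readings.** A reader might infer that 11.4 ends follow-up of every non-serious AE at the last visit. It does not: resolution or study termination can end it sooner, and for AE withdrawals 11.2.7 and 12 say otherwise. A reader might also infer that the trial's comparisons are compromised. Nothing here touches randomisation, the efficacy assessments, alpha or power, and both rules apply alike to all arms.

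**Conclusion.** Both inconsistencies are in the current text, and both are minor. Applied literally, 11.4 would let a site stop following an unresolved non-serious AE that led to withdrawal at the last visit, contrary to 11.2.7 and 12. How often this would happen cannot be derived from the protocol. Section 10.1.5 puts EOS nominally 7 days early for completers who attend it, on the assumption of 24 doses given on schedule and EOT on day 7. It leaves no compliant day when EOT/ET falls 9 or more days after the last dose. The effect is confined to safety follow-up and the length of the AE collection window. The Section 11.5 references are clerical.

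**What to change.** - **Section 11.4:** at the end of the general AE rule add: *except that AEs leading to discontinuation of study drug or withdrawal from the study, including Table 3 laboratory stops, are followed until recovery or stabilisation as stated in Sections 11.2.7 and 12*. Naming both discontinuation of drug and withdrawal from the study matters: 11.2.7 and 12 speak of the study, while 11.1.1 classes laboratory-driven stops of treatment as AE withdrawals.
- **Section 10.1.5:** replace the last-dose anchor with *after completing the EOT/ET assessments*, keeping 4 weeks (± 4 days).
- **Sections 6.3.2, 8.3.5, 8.3.6 and 11.2.3:** change the Section 11.5 references on withdrawal or discontinuation to Section 12.

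The cost is text edits only. No scheduled visit, sample or test is added: 11.2.7 and 12 already call for the longer follow-up, and the Schedule of Events already places EOS 4 weeks after EOT/ET.

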11.5 Other Reportable Events

Certain events that occur in the absence of an AE should be reported to the Sponsor. These include the following events:

- Pregnancy exposure (patient becomes pregnant while taking study drug). Should a female patient or partner of a male patient become pregnant during the study, the patient will inform the Investigator. The patient will be asked to follow up with the study site to report the eventual outcome of the pregnancy. The information will be tracked by the Sponsor.
- Overdose of study medication (defined as dosing ≥ 2 fold above intended weekly dose) occurring as a result of dosing amount error or timing error should be reported on the eCRF. The CRO Medical Monitor should be contacted if an overdose occurs. Any adverse outcomes of overdose should be recorded as AEs/SAEs according to the procedures described in Section 11.2.
- Lactation exposure (subject was taking study drug while nursing an infant)
- Accidental exposure (someone other than the study subject was exposed to study drug)
- Other medication errors that potentially place subjects at greater risk of harm than was previously known or recognized (e.g., study drug was administered via an incorrect route)

12 WITHDRAWAL OF PATIENTS

All patients who receive study drug should remain in the study whenever possible. However, patients are free to withdraw consent and/or discontinue participation in the study at any time, without prejudice to further medical care.

A patient's treatment and participation in the study may also be discontinued at any time at the discretion of the Investigator, CRO Medical Monitor, or Idera. Justifiable reasons to discontinue a patient from treatment and the study may include, but are not limited to the following:

- The patient was erroneously included in the study (i.e., did not meet eligibility criteria)
- The patient experiences an SAE assessed as possibly or probably related to study drug
- The patient is unable to comply with the requirements of the protocol
- The patient participates in another investigational study
- The patient withdraws consent
- The patient becomes pregnant
- A patient for whom the blind is intentionally broken

Patients who are withdrawn from treatment should complete the EOT/ET Visit 26/Week 25 assessments within 5 days of notification of withdrawal and the EOS Visit 27/Week 29 at 4 weeks (\pm 4 days) after the ET Visit (see Sections 10.1.4 and 10.1.5 for information regarding the EOT/ET and EOS Visits, respectively). A patient who completes the initial portion of the study (through the EOT Visit 26/Week 25) and is then lost to follow-up will not be considered to have prematurely withdrawn.

A patient will be considered "discontinued due to an AE" if they withdraw from the study due to any AE, regardless of whether or not the AE is considered related to investigational product. If the patient withdraws from the study due to an AE, the Investigator should arrange for the patient to be followed appropriately until the AE has resolved or stabilized (in the opinion of the Investigator).

The Investigator will document the reason(s) for treatment or study discontinuation on the eCRF. Idera and the CRO Medical Monitor should be informed when a patient is withdrawn from the study.

13 DATA COLLECTION, QUALITY ASSURANCE, AND MANAGEMENT

13.1 Data Collection and Recording

The Investigator or personnel designated by the Investigator will perform primary data collection based on source document hospital or clinic records or other source documentation. All required study information must be recorded on the appropriate eCRF. The study monitor will review eCRFs for accuracy and completeness to ensure maximum data integrity. In addition, as the person ultimately responsible for the accuracy of all eCRF data, the Investigator will provide electronic endorsement that the data on the eCRFs are accurate and complete. Data processed at a central laboratory (e.g., safety laboratory tests and bioanalytical data) will be transferred electronically. An IXRS will be used to allocate the randomized treatments to patients as they are enrolled. The randomized treatment assignments will be transferred electronically for integration with the clinical study data at the appropriate time.

13.2 Data Quality Assurance

The eCRFs will be reviewed by a CRO study monitor against the source notes for identification and clarification of any discrepancies. Automated quality assurance programs will be in place to identify discrepancies, such as missing data, selected protocol violations, out of range data, and other data inconsistencies. Requests for data clarification or correction will be documented using an electronic data query and forwarded to the Investigator or study coordinator for resolution. All changes to the eCRFs will be tracked to provide an audit trail.

The Investigator must make study data accessible to the study monitor, to other authorized representatives of Idera, and to the appropriate regulatory authority inspectors. Audits for quality assurance of the database may be performed according to relevant standard operating procedures within the CRO or at the request of Idera.

13.3 Data Management

Idera, in close collaboration with any designee, will be responsible for:

- database creation and validation
- eCRF review and data validation
- query resolution
- data analysis and reporting

A detailed Data Management Plan will be prepared separately and approved by Idera.

13.4 Protocol Violations

Prior to unblinding the study, Idera will review the protocol violations that occur during the study. A determination will be made as to which violations are considered to be major or would potentially impact efficacy assessments. Patients with such violations will not be included in the Per Protocol analysis, as per Section 14.3.

Examples of violations that would be considered to impact efficacy assessments would be:

- Change in background DM therapy during the study period
- Wrong study treatment was given
- Receiving <80% of planned doses of study treatment while on study.

14 STATISTICAL METHODS AND PLANNED ANALYSES

14.1 General Considerations

Continuous endpoints will be summarized descriptively. Categorical endpoints will be summarized by the number and percentage of patients in each category and 95% confidence intervals for the proportion.

14.2 Determination of Sample Size

A simulation was conducted in which one of the IMO-8400 groups exhibits a mean decrease of 7 points in CDASIV2-Activity score over 24 weeks, assuming a baseline mean of 25 and a standard deviation of 8.5 and the placebo group exhibits no mean decrease. Correlation between baseline CDASIV2-Activity score and Week 25 mCDASIV2-Activity score was assumed to be 0.4 for IMO-8400 treated patients and 0.7 for placebo treated patients. Using a repeated measures mixed model (RMMM) to analyze monthly mCDASIV2-Activity assessments, 10 patients with complete data yields 81.2% power to detect such a 7-point difference between groups at Week 25, using a 1-sided test with an alpha of 0.05. A 20% rate of patient dropout was assumed, yielding the final sample size of 12 subjects per treatment group.

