- Serum samples for presence of autoantibodies associated with idiopathic inflammatory myopathies, including, but not necessarily limited to, the following: anti-MDA-5, anti-Mi-2, anti-TIF1 γ , anti-NXP2, anti-SAE1, anti-SAA 60, anti-Ro/SSA 52, anti-SSB/La, anti-Sm, anti-RNP, anti-Scl-70, anti-ribosomal-P, anti-chromatin, anti-Jo-1, anti-PL-7, and anti-PL-12.

Immunogenicity:

- Serum samples for antibodies to IMO-8400 and antibodies to double-stranded deoxyribonucleic acid (dsDNA)

Statistical Methods

Determination of Sample Size

This study has approximately 80% power to detect a difference of 7 points in change from baseline on the mCDASIV2-Activity score at Week 25 using a 1-sided test with an alpha of 0.05.

Randomization

Randomization will be performed centrally in a 1:1:1 ratio (placebo or IMO-8400 at 0.6 mg/kg or 1.8 mg/kg) and will be stratified by baseline CDASIV2-Activity score (15 to 20 vs. \geq 21).

Analysis Populations

- Safety Population and Intent-to-Treat Population (ITT): All patients who received at least 1 injection of study medication
- Per Protocol Population (PP): All patients who received at least 20 doses of study drug as assigned, completed the EOT Visit 26/Week 25, and had no major protocol violations that would potentially influence treatment effect (as determined by review by Idera prior to unblinding)

Safety analyses will be performed using the Safety Population. The efficacy, PD, disease-specific autoantibodies, and immunogenicity assessments will be analyzed for the ITT population; key endpoints may be also analyzed for the PP Population as specified in the Statistical Analysis Plan (SAP).

Primary Safety and Tolerability Endpoints

- Number of patients discontinuing treatment due to AEs

- Frequency and severity of AEs
- Physical examination findings, including vital signs
- Standard laboratory safety tests including hematology, chemistry, coagulation and urinalysis
- Assessment of ISRs
- ECG findings
- Laboratory safety assessments including CH50, C3, C4, troponin, CRP, albumin, globulin, A:G ratio, proteinuria, eGFR, and platelet count

Primary Efficacy Endpoint

- Change from baseline in mCDASIV2-Activity score

Safety Analyses

Adverse events will be coded using the Medical Dictionary for Regulatory Activities (MedDRA) and tabulated by event, grade, and relationship to study therapy. Safety analyses will be descriptive in nature; no statistical hypothesis testing will be performed.

Efficacy Analyses

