14.4.4 Efficacy Analyses

The primary efficacy endpoint will be assessed via an RMMM. An appropriate covariance structure for repeated measures will be used. The difference between each IMO-8400 treatment group and placebo at Week 25 will be assessed. The overall alpha level will be controlled using the Bonferroni-Holm step-down method. Further details of this analysis will be described in the SAP. A sensitivity analysis will be performed to test the effect of important covariates on the effect of IMO-8400 using an RMMM.

Differences in response rate between the IMO-8400 treatment groups and placebo will be assessed via logistic regression.

The MMT8, TUG, 4 stair climb test, timed 10MWR test, serum CK, ALD, LDH, AST, ALT, SF-36, and 5-D Itch Scale will be analyzed in a similar manner to the primary endpoint.

For the proportion of patients who meet the IMACS 2004 DOI (Rider 2004) at EOT, logistic regression will be performed.

All efficacy endpoints will also be summarized descriptively by treatment group and nominal visit. Other exploratory and sensitivity analyses will be specified in the SAP in addition to further details regarding the statistical methodology.

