14.5 Significance Levels

Statistical analyses will use a 1-sided test with alpha set at 0.05.

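### The 81.2% power is computed at 1-sided 0.05, but Bonferroni-Holm over two doses makes 0.025 the working threshold; in the planned scenario power is about 70%

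*Protocol*

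**What the plan says.** Section 14.2 bases the sample size on a simulation in which "one of the IMO-8400 groups exhibits a mean decrease of 7 points in CDASIV2-Activity score over 24 weeks" and placebo does not change. The assumed baseline mean is 25 and the SD 8.5. The correlation between baseline and Week 25 is 0.4 on active drug and 0.7 on placebo. With 10 completers, read as per group, the repeated measures mixed model "yields 81.2% power to detect such a 7-point difference between groups at Week 25, using a 1-sided test with an alpha of 0.05". Allowing for 20% dropout, the plan is 12 patients per group. The synopsis makes the same claim for the study as a whole: "This study has approximately 80% power to detect a difference of 7 points in change from baseline on the mCDASIV2-Activity score at Week 25".

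Section 14.4.4 defines the primary analysis: "The difference between each IMO-8400 treatment group and placebo at Week 25 will be assessed". There are two IMO-8400 groups, so there are two primary comparisons. It continues: "The overall alpha level will be controlled using the Bonferroni-Holm step-down method". The synopsis repeats this. Section 14.5 sets the level: "Statistical analyses will use a 1-sided test with alpha set at 0.05". The sample size text mentions neither Holm, nor a divided alpha, nor a second comparison.

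**The concern.** The power statement and the primary test use different thresholds. Holm with two comparisons at an overall 0.05 tests the smaller p-value at 0.025. The larger one is tested at 0.05 only after the first has been rejected. When one dose works and the other does not, the 0.05 step helps the effective dose only if the ineffective dose has already been rejected at 0.025, which is rare.

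The stated 81.2% therefore describes a test the trial will not perform. The protocol relies on this figure in Section 14.2, in the synopsis and in the design rationale (Section 17.2.1), which says the study is powered for a 7-point effect. A reader of a negative result would credit the trial with a better chance of finding that effect than it has.

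**Working it through.** **Inputs (Section 14.2 unless noted).** Difference 7 points; SD 8.5; correlation 0.4 (active) and 0.7 (placebo); 10 completers per group; power 81.2% at 1-sided 0.05. Two comparisons under Holm (Section 14.4.4), overall 1-sided alpha 0.05 (Section 14.5), allocation 1:1:1 (synopsis).

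**1. Can 81.2% be reproduced at 0.05?** For a single comparison with 10 per arm, power ≈ Φ(7/SE − 1.645).

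- Week 25 score alone: SE = √(2 × 72.25/10) = 3.80; 7/3.80 = 1.84; power 58%.
- Change score, variance 2 × 72.25 × (1 − r): SE = √((86.70 + 43.35)/10) = 3.61; 7/3.61 = 1.94; power 62%.
- Baseline-adjusted score, variance 72.25 × (1 − r²): SE = √((60.69 + 36.85)/10) = 3.12; 7/3.12 = 2.24; power 72%.
- Simulated baseline-adjusted repeated measures models with a linear decline over six monthly visits: 65% to 77%, depending on the covariance.

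None of these reaches 81.2% with both stated correlations. Using 0.7 in both arms gives about 82%, but that drops the stated 0.4. The protocol does not give the visit means, covariance or model of its simulation, so this does not prove 81.2% wrong. The next steps accept it.

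**2. Signal implied by 81.2% at 0.05.** Noncentrality δ = z(0.95) + z(0.812) = 1.645 + 0.885 = 2.530 (normal). With t distributions it is 2.631 (18 df), 2.60 (26 df) and 2.584 (33 df).

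**3. Same signal at 0.025.**

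- Normal: Φ(2.530 − 1.960) = Φ(0.570) = 71.6%.
- t: 70.2% (18 df), 70.6% (26 df), 70.8% (33 df).

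**4. Full Holm procedure, simulated.** The two comparisons share the placebo arm, so with equal arms their test statistics correlate at 0.5. Ranges below run from 26 df to the normal limit.

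| True effect in the other dose | Power for the 7-point dose | At least one rejection |
|---|---|---|
| None | 70.6% to 71.6% | about the same |
| Half (normal limit only) | 72.7% | 73.8% |
| Equal (7 points) | 76.6% to 77.3% | 84.1% to 85.5% |

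In the first row Holm adds less than 0.1 percentage point to the simple 0.025 calculation (71.62% against 71.57% in the normal case). Lowering the correlation to 0.3 gives 71.7%.

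**5. Size of the gap.** The miss probability is 100 − 81.2 = 18.8% as stated and 100 − 70.6 = 29.4% at 26 df under the planned test.

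**6. Completers needed to keep 81.2% at 0.025.** 10 × ((1.960 + 0.885)/2.530)² = 10 × 1.265 = 12.65, so 13 per group. With 20% dropout, 13/0.8 = 16.25, so 17 randomized per group, or 51 in total against the planned 36.

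**The case against.** There are four serious replies.

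*Holm may already be inside the simulation.* Section 14.2 does not say in terms that a single comparison was made, and 0.05 could be the overall level of a three-arm simulation. This cannot be excluded from the protocol alone. However, the text describes a 1-sided test at 0.05 and nothing more. With the stated inputs, models run at the full 0.05 already fall short of 81.2%, and at 0.025 the baseline-adjusted ones give only about 52% to 68%. A hidden 0.025 is therefore unlikely.

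*About 70% is the least favourable case.* This is true: power rises with the effect of the other dose. If both doses have the full 7 points, the synopsis figure holds for at least one success. But Section 14.2 assigns the effect to one group and states none for the other. With half the effect in the second dose, the chance of any success is still only about 74%.

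*The replacement figure rests on a number that could not be reproduced.* This also stands, and it is why the request is to rerun the simulation rather than simply write in 70%. The inconsistency itself needs only the stated power and the change of alpha.

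*The trial is a small Phase 2 study and no error rate is inflated.* Holm does control the type I error, no estimate is biased, and the analysis can be run as written. That limits the harm to the planning claim, but it does not make the claim correct. Nor is this a detail to leave to the SAP, because the protocol itself fixes the scenario, the alpha, the multiplicity method and the power.

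**Conclusion.** The concern holds. The power in Section 14.2 and the synopsis is calculated at 1-sided 0.05, while the primary test in Section 14.4.4 requires 0.025 in practice when one dose is effective. Power for the planned scenario is 70% to 72%, about 10 points below the stated 81.2%. This rests on three assumptions: the sponsor's 81.2% is correct for a single test at 0.05, the other dose has no effect, and the two comparisons share one placebo arm of equal size. The result hardly changes with the error degrees of freedom or the correlation between the comparisons. It does change with the effect of the other dose, which the protocol leaves unstated.

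**What to change.** Rerun the simulation with all three arms and the Holm procedure. State the effect assumed for the second dose and whether power means success for a given dose or for at least one. Replace the figure in Section 14.2 and the synopsis with the result, expected to be about 70% for one effective dose if 81.2% was right. In Section 14.5, add that 0.05 is the overall level across the two dose comparisons. This costs a rerun and some wording, needs no extra patients, and leaves a less favourable power statement.

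Two alternatives keep the stated power, each at a price:

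- Replace Holm with a fixed sequence: one dose named in advance and tested at 1-sided 0.05, the other tested only if the first succeeds. The first comparison is then made at the alpha used in the calculation, but the second dose cannot be claimed if the first fails. Section 14.4.4 and the synopsis must then change too, and the choice must be fixed before unblinding.
- Keep Holm and enlarge the trial to about 13 completers, or 17 randomized, per group.
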